11.1.9 Laboratory Evaluations

The laboratory evaluations listed in Table 1, including special tests for vitamin deficiencies (Folic Acid, Vitamin B6, Vitamin B12, Methylmalonic Acid (MMA), and Homocysteine) will be performed by a central laboratory to be designated by Sponsor, at the times indicated in [Table 2](#). No other formal assessment of laboratory evaluations is scheduled, but will be done as subject's condition mandates and performed as an element of routine care.

Table 1. Laboratory Evaluations

Hematology	Blood Chemistry	Special Tests	Urinalysis
Hemoglobin	Glucose	Folic Acid,	pH
Hematocrit	Creatinine	Vitamin B6,	Specific Gravity
White blood count	Creatinine kinase	Vitamin B12,	Glucose
(WBC) with differential	Alkaline phosphatase	Methylmalonic Acid	Protein
Erythrocyte count (RBC)	Total bilirubin	(MMA), and	Microscopic
Platelet count	Serum glutamic-	Homocysteine levels	Examination
Mean corpuscular volume	pyruvic transaminase		Urine Pregnancy
(MCV)	(SGPT/ALT)		Test -
Mean corpuscular	Serum glutamic-		For subjects who are
hemoglobin (MCH)	oxaloacetic		of child-bearing
Mean corpuscular	transaminase		potential, a negative
hemoglobin	(SGOT/AST)		urine pregnancy test
concentration (MCHC)	Gamma-glutamyl		is required on the
	transpeptidase		day of the procedure
	(GGT)		prior to any
	Total protein		radiological check
	Uric acid		of tube placement.
	Calcium		
	Sodium		
	Potassium		
	Chloride		
	Serum urea nitrogen		
	(BUN)		
	Bicarbonate		
	Lactate dehydrogenase		
	(LDH)		
	Total cholesterol		
	Triglycerides		
	Albumin		
	Pregnancy Test for		
	applicable subjects ^a		
	Beta human chorionic		
	gonadotropin		
	(β -hCG)		

a. For all females of child-bearing potential, at end of study.

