8.0 Analysis Variables: Definitions, Derivations, Calculations and Conventions

8.1 Subject Disposition

8.1.1 Subject Samples

There will be three hierarchical subject samples of interest.

The "All Subjects Consented" subject sample will be used to summarize subject disposition and will consist of all subjects who:

- Gave their informed consent.

The Safety subject sample will consist of all subjects who:

- Were in the "All Subjects Consented" subject sample and
- Received at least 1 infusion of 3005 study drug

The Safety subject sample will be used for all analyses of safety unless noted otherwise.

The Efficacy subject sample will consist of all subjects who:

- Were in the Safety subject sample and
- Have at least 1 efficacy assessment in 3005

The Efficacy subject sample will be used for all analyses of efficacy unless noted otherwise.

For subjects enrolled in the United States, efficacy assessments were added with Protocol Amendment 4. To evaluate efficacy and safety in these subjects, analyses will be completed including only the subjects in the relevant subject sample who were enrolled in the United States (the "US Subset").

To evaluate the association between polyneuropathy events and vitamin deficiencies, additional analyses will be completed for the subset of subjects who experienced a TEAE coded to either the Standardized MedDRA Query (SMQ) of Peripheral Neuropathy – narrow search or Guillain-Barre Syndrome – narrow search (the "Narrow Polyneuropathy Subset").

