For a missing/incomplete stop date the maximum of the following will be imputed:

- The minimum of the latest possible stop date and the date of last administration of investigational study drug
- The earliest possible stop date
- The earliest possible start date

Here, the earliest (latest) possible date is defined as:

- The date itself if it is possible
- The date of the first (last) day of the month, if month and year are available but the day is missing
- The date of the first (last) day of the year, if year is available but day and month are missing
- A very early (late) date, for example, 01JAN1000 (01JAN3000), if the date is completely missing

From this data the following will be determined and used for presentation in the applicable tables and listings:

- Treatment-Emergent Adverse Events (TEAEs): Defined as AEs which started on or after the Date of the First 3005 LCIG Infusion and within 30 days of the Date of the Last 3005 PEG-J Exposure.
- Treatment-Emergent Serious Adverse Events (TESAEs): Defined as TEAEs regarded by the Investigator as Serious.
- TEAEs that are at least possibly related to the therapeutic system: Defined as TEAEs assessed as having a "Possible" or "Probable" relationship to the investigational therapeutic system and includes those events where the relationship is missing.
- Severe TEAEs: Defined as TEAEs assessed as being "Severe" in intensity and includes those events where the severity is missing.
- TEAEs that led to premature discontinuation: Selected as those events where: "Led to Study Termination" is indicated as "Yes."
- TEAEs with fatal outcome as reported on the "Adverse events" CRF.
- TEAEs in the following categories have been defined as TEAEs of special interest:
 - Procedure and device associated events
 - Polyneuropathy (broad search as well as narrow search)
 - Weight loss

- Cardiovascular fatalities
- Respiratory tract aspiration including aspiration pneumonia/pneumonitis

TEAEs are included in a category of special interest based on their PT and, in the case of cardiovascular fatalities, their outcome. The list of PT's assigned to each category is included as Appendix 12.4. Only TEAEs where an outcome of "Fatal" has been reported on the "Adverse Event" CRF are to be included in the category of cardiovascular fatalities. All events with PT's other than those assigned to the procedure and device associated AESI category will be included in summaries of events that are not procedure and device related.

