AET006	14.3__1.2.4.9	Number and Percent of Subjects with Treatment-Emergent Adverse Events of Special Interest Related to Weight Loss SAFETY SAMPLE – US SUBSET
AET006	14.3__1.2.4.10	Number and Percent of Subjects with Treatment-Emergent Adverse Events of Special Interest Related to Cardiovascular Fatalities SAFETY SAMPLE – US SUBSET
AET006	14.3__1.2.4.11	Number and Percent of Subjects with Treatment-Emergent Adverse Events of Special Interest Related to Aspiration SAFETY SAMPLE – US SUBSET
AEL003	14.3__2.1	Listing of Subject Deaths SAFETY SAMPLE
AEL004	14.3__2.2	Listing of Serious Adverse Events SAFETY SAMPLE
AEL005	14.3__2.3	Listing of Adverse Events Leading to Study Termination SAFETY SAMPLE
AEL006	14.3__2.4	Listing of Adverse Events of Special Interest Related to Procedure and Device SAFETY SAMPLE
AEL006	14.3__2.5	Listing of Adverse Events of Special Interest Related to Polyneuropathy SAFETY SAMPLE
AEL006	14.3__2.6	Listing of Adverse Events of Special Interest Related to Weight Loss SAFETY SAMPLE
AEL006	14.3__2.7	Listing of Adverse Events of Special Interest Related to Cardiovascular Fatalities SAFETY SAMPLE
AEL006	14.3__2.8	Listing of Adverse Events of Special Interest Related to Aspiration SAFETY SAMPLE
LBT001	14.3__4.1.1	Number and Percentage of Subjects with Potentially Clinically Significant Hematology Laboratory Parameters SAFETY SAMPLE
LBL002	14.3__4.1.2	Listing of Potentially Clinically Significant Hematology Laboratory Parameters SAFETY SAMPLE
LBT001	14.3__4.2.1	Number and Percentage of Subjects with Potentially Clinically Significant Chemistry Laboratory Parameters SAFETY SAMPLE
LBL002	14.3__4.2.2	Listing of Potentially Clinically Significant Chemistry Laboratory Parameters SAFETY SAMPLE
LBT002	14.3__4.3.1	Summary of Quantitative Special Laboratory Parameters for Determination of Vitamin Deficiency SAFETY SAMPLE

SAP Table Code	Table Number	Table Title
LBT003	14.3__4.3.2	Number and Percent of Subjects with Quantitative Special Laboratory Parameters for Determination of Vitamin Deficiency Outside of the Reference Range SAFETY SAMPLE
LBT002	14.3__4.4.1	Summary of Quantitative Special Laboratory Parameters for Determination of Vitamin Deficiency SAFETY SAMPLE – NARROW POLYNEUROPATHY SUBSET
LBT003	14.3__4.4.2	Number and Percent of Subjects with Quantitative Special Laboratory Parameters for Determination of Vitamin Deficiency Outside of the Reference Range SAFETY SAMPLE – NARROW POLYNEUROPATHY SUBSET

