10058530	Peripheral nerve palsy	
10034591	Peripheral nervous system function test abnormal	
10054808	Peripheral paralysis	
10056673	Peripheral sensorimotor neuropathy	
10034620	Peripheral sensory neuropathy	
10034701	Peroneal nerve palsy	
10059923	Pharyngeal hypoaesthesia	
10036105	Polyneuropathy	
10036111	Polyneuropathy idiopathic progressive	
10036800	Progressive bulbar palsy	
10037114	Pseudobulbar palsy	
10049680	Quadriparesis	
10037714	Quadriplegia	
10037779	Radiculopathy	
10038254	Reflexes abnormal	
10038669	Respiratory arrest	
10038695	Respiratory failure	
10070833	Respiratory muscle weakness	
10038708	Respiratory paralysis	
10062162	Sensorimotor disorder	
10040026	Sensory disturbance	
10048871	Sensory integrative dysfunction	
10061567	Sensory level abnormal	
10040030	Sensory loss	
10041466	Speech disorder	
10061551	Spinocerebellar disorder	
10058560	Tandem gait test abnormal	
10068008	Trigeminal nerve paresis	
10049788	Trigeminal palsy	
10045380	Ulnar neuritis	
10045555	Unresponsive to stimuli	

Code	Preferred Term	Narrow Search (N)
10059101	Vibration test abnormal	
10050040	VII th nerve paralysis	
10047641	VI th nerve paralysis	
10071044	VI th nerve paresis	

Peripheral Neuropathy SMQ (20000034)

Code	Preferred Term	Narrow Search (N)
10066699	Acute polyneuropathy	N
10002027	Amyotrophy	N
10070439	Autoimmune neuropathy	N
10003882	Axonal neuropathy	N
10004846	Biopsy peripheral nerve abnormal	N
10067502	Decreased vibratory sense	N
10061811	Demyelinating polyneuropathy	N
10018767	Guillain-Barre syndrome	N
10051307	Ischaemic neuropathy	N
10057332	Loss of proprioception	N
10049567	Miller Fisher syndrome	N
10065579	Multifocal motor neuropathy	N
10028570	Myelopathy	N
10029175	Nerve conduction studies abnormal	N
10029223	Neuralgia	N
10029240	Neuritis	N
10071579	Neuronal neuropathy	N
10029331	Neuropathy peripheral	N
10034580	Peripheral motor neuropathy	N
10034591	Peripheral nervous system function test abnormal	N
10056673	Peripheral sensorimotor neuropathy	N
10034620	Peripheral sensory neuropathy	N
10036105	Polyneuropathy	N
10064135	Polyneuropathy chronic	N
10036111	Polyneuropathy idiopathic progressive	N

Code	Preferred Term	Narrow Search (N)
10068886	Radiation neuropathy	N
10062162	Sensorimotor disorder	N
10040026	Sensory disturbance	N
10040030	Sensory loss	N
10067722	Toxic neuropathy	N
10003084	Areflexia	
10056339	Autonomic failure syndrome	
10061666	Autonomic neuropathy	
10070237	Burning feet syndrome	
10006784	Burning sensation	
10013886	Dysaesthesia	

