10014431	Electromyogram abnormal	
10017062	Formication	
10017577	Gait disturbance	
10068912	Genital hypoaesthesia	
10020937	Hypoaesthesia	
10021089	Hyporeflexia	
10021118	Hypotonia	
10027910	Mononeuritis	
10062203	Mononeuropathy	
10027918	Mononeuropathy multiplex	
10061296	Motor dysfunction	
10028289	Muscle atrophy	
10028372	Muscular weakness	
10056677	Nerve degeneration	
10062284	Neuromuscular toxicity	
10029323	Neuromyopathy	
10029332	Neuropathy vitamin B6 deficiency	
10029350	Neurotoxicity	
10033775	Paraesthesia	
10067633	Peripheral nerve lesion	
10058530	Peripheral nerve palsy	
10071663	Peripheral nerve paresis	

Code	Preferred Term	Narrow Search (N)
10034699	Peroneal muscular atrophy	
10034701	Peroneal nerve palsy	
10064964	Phrenic nerve paralysis	
10054786	Skin burning sensation	
10068015	Temperature perception test decreased	
10052492	Tinel's sign	
10045380	Ulnar neuritis	

3. Weight loss (CMQ 80000109).

Code	Preferred Term
10000159	Abnormal loss of weight
10002647	Anorexia and bulimia syndrome
10002649	Anorexia nervosa
10060961	Appetite disorder
10005895	Body mass index decreased
10006895	Cachexia
10061428	Decreased appetite
10012775	Diet refusal
10013950	Dysphagia
10014062	Eating disorder
10061832	Eating disorder symptom
10050366	Fear of eating
10053050	Gastrointestinal tube insertion
10052592	Gastrostomy tube insertion
10063743	Hypophagia
10021577	Inadequate diet
10061273	Malnutrition
10026820	Marasmus
10028155	Multi-vitamin deficiency
10065026	Nutritional condition abnormal
10029861	Nutritional support
10051284	Parenteral nutrition

Code	Preferred Term
10050086	Poor weight gain neonatal
10041954	Starvation
10048828	Underweight
10056814	Weight abnormal
10047894	Weight decrease neonatal
10047895	Weight decreased
10049040	Weight fluctuation
10047897	Weight gain poor
10047901	Weight loss diet

4. Cardiovascular fatalities: major adverse cardiovascular events (MACE) MI CMQ (80000076) and the outcome of the AE was fatal.

Code	Preferred Term
10051592	Acute coronary syndrome
10000891	Acute myocardial infarction
10054015	Agonal rhythm
10002388	Angina unstable
10003225	Arteriospasm coronary
10005468	Blood creatine phosphokinase abnormal
10005470	Blood creatine phosphokinase increased
10005472	Blood creatine phosphokinase MB abnormal
10005474	Blood creatine phosphokinase MB increased
10007515	Cardiac arrest
10049993	Cardiac death
10007548	Cardiac enzymes increased
10007617	Cardio-respiratory arrest
10007625	Cardiogenic shock

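### The vitamin analysis in polyneuropathy cases does not admit a subject whose only qualifying event is coded as vitamin B6 deficiency neuropathy

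*SAP*

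**What the plan says.** SAP 8.1.1 gives the purpose of the subset: "To evaluate the association between polyneuropathy events and vitamin deficiencies, additional analyses will be completed for the subset of subjects who experienced a TEAE". Under the entry rule in the same section, that event has to be "coded to either the Standardized MedDRA Query (SMQ) of Peripheral Neuropathy – narrow search or Guillain-Barre Syndrome – narrow search". One treatment-emergent event with a narrow PT from either query is enough.

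SAP 12.4, item 2, lists the PTs of both queries and marks narrow ones with N. The PT "Neuropathy vitamin B6 deficiency" (10029332) is in the Peripheral Neuropathy list without an N and is absent from the Guillain-Barre list. The general PT "Neuropathy peripheral" (10029331) carries an N in the Peripheral Neuropathy list.

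Deficiency itself is a laboratory finding. Protocol 11.1.9 provides for "special tests for vitamin deficiencies (Folic Acid, Vitamin B6, Vitamin B12, Methylmalonic Acid (MMA), and Homocysteine", and Protocol Table 2 schedules these at baseline, at each 6-monthly visit and at termination. SAP 12.2 plans four outputs for the subset:

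- 14.3__4.4.1, titled "Summary of Quantitative Special Laboratory Parameters for Determination of Vitamin Deficiency SAFETY SAMPLE – NARROW POLYNEUROPATHY SUBSET"
- 14.3__4.4.2, subjects with values outside the reference range
- 14.3__4.4.3, a chemistry listing
- 14.1__1.4.4, a concomitant medication listing

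The same two vitamin tables are also planned for the whole Safety sample (14.3__4.3.1 and 14.3__4.3.2). None is planned for broad-search cases.

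**The concern.** The PT left out is the only one in either polyneuropathy list that names a vitamin deficiency, and the subset exists to study vitamin deficiency. Two subjects with the same neuropathy and the same low B6 result can be treated differently: one is a case because the investigator reported a general term, the other is not because the investigator named the cause.

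The rule for counting cases then depends partly on the factor being studied. The output at stake is the proportion of subset subjects with B6 below the reference range in Table 14.3__4.4.2, along with the B6 summary in 14.3__4.4.1. Polyneuropathy is an adverse event of special interest (Protocol 12.1.4), and these two tables are the only ones planned that show vitamin results by neuropathy status.

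**Working it through.** The plan states no figure on this point, so there is none to reproduce. The check has three parts.

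**1. Does the PT qualify through either list?** Counts from SAP 12.4, item 2:

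- Peripheral Neuropathy query: 30 narrow PTs and 35 broad-only PTs.
- Guillain-Barre query: 4 narrow PTs, of which 3 (Demyelinating polyneuropathy, Guillain-Barre syndrome, Miller Fisher syndrome) are also narrow in the other list.
- Distinct narrow PTs: 30 + 4 − 3 = 31.

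Code 10029332 is not among the 31. Adding it would make 32.

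**2. Could the missing N be a fault in reading the PDF?** The Peripheral Neuropathy list shows its 30 narrow PTs in alphabetical order. The alphabet then restarts for the 35 broad-only PTs, and the B6 term stands in its alphabetical place in that second block, between Neuromyopathy and Neurotoxicity. The classification is what the plan intends.

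**3. What happens to comparable cases?**

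| Reported PT | Narrow? | In the vitamin subset? |
|---|---|---|
| Neuropathy peripheral | Yes | Yes |
| Toxic, Radiation or Ischaemic neuropathy | Yes | Yes |
| Neuralgia, Myelopathy, Sensory disturbance | Yes | Yes |
| Neuropathy vitamin B6 deficiency, alone | No | No |
| Neuropathy vitamin B6 deficiency plus any narrow PT | Yes, through the second PT | Yes |

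Naming a cause does not by itself remove a PT from the narrow list, and less specific terms are on it.

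**Illustration of size.** The documents give neither the subset size nor the number of events with this PT, so the following rests on assumptions. Let *m* be the subset size as defined, *x* the number with low B6 (assumed 30% of *m*), and *k* the number of subjects whose only qualifying event is the B6 PT, all assumed to have low B6. The share goes from *x*/*m* to (*x* + *k*)/(*m* + *k*).

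| *m*, *x* | *k* = 0 | *k* = 1 | *k* = 2 | *k* = 3 |
|---|---|---|---|---|
| 10, 3 | 30.0% | 4/11 = 36.4% | 5/12 = 41.7% | 6/13 = 46.2% |
| 20, 6 | 30.0% | 7/21 = 33.3% | 8/22 = 36.4% | 9/23 = 39.1% |
| 30, 9 | 30.0% | 10/31 = 32.3% | 11/32 = 34.4% | 12/33 = 36.4% |

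With *k* = 0 nothing changes. The upward direction depends on the added subjects having a low value on record after baseline. One added subject without it would give 6/21 = 28.6% in the middle row.

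**The case against.** The case for leaving the definition alone has real substance.

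- **Few subjects can be lost.** Any of 31 PTs admits a subject. The scheduled neurological examination generates adverse events of its own (Protocol 11.1.8, SAP 8.5.5.7), and PTs such as Sensory loss and Decreased vibratory sense are narrow. This stands, but not completely: Protocol 12.1.1 asks investigators to report a diagnosis as one term instead of its separate signs, so a sole B6 entry is possible.
- **Deficiency is read from the laboratory.** A subject with low B6, B12 or folate and a general neuropathy PT is a case, and the low value is counted. No listed PT names a B12 or folate neuropathy. This stands in full. A reader might infer that the cases most relevant to the question are left out; the documents do not support that.
- **The event stays visible.** SAP 8.5.1 analyses "Polyneuropathy (broad search as well as narrow search"), so it would appear in Table 14.3__1.2.2.12, and the subject's vitamin values enter the full-sample tables. True, but neither output links the event to the vitamin result.
- **Adding a PT that names the deficiency builds in the association.** This is a fair caution, and a reason to prefer a sensitivity analysis if the sponsor wants the standard search as the main one. Yet the rule as written has the opposite dependence, and deficiency would still be judged from laboratory values.
- **An unmodified standard search is reproducible, and other neuropathy PTs are also broad-only** (Autonomic neuropathy and Mononeuropathy, for example). This is a good reason not to alter Table 14.3__1.2.2.13, a general narrow-search table to which the vitamin rationale does not apply. It has less force for a subset built to answer one question about vitamins.

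**Conclusion.** The point holds in a limited form. By its own definition the subset excludes a subject whose only qualifying event is PT 10029332, although the same neuropathy under a general term would qualify. In this one analysis, case status depends on whether the investigator named the B6 cause.

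A reader might go further and conclude that the low-B6 share is biased downward. The documents do not show that. It would require at least one subject with this PT, no narrow PT, and a low B6 value, and nothing in the plan indicates that such a subject exists. If there are any, the share is understated by an unknown amount; if there are none, the results are the same. The outputs concerned are descriptive, with no test attached. This is a cheap improvement, not a flaw that undermines the safety analysis.

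**What to change.** For the vitamin analysis only (Tables 14.3__4.4.1 and 14.3__4.4.2 and listings 14.1__1.4.4 and 14.3__4.4.3), do one of the following:

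1. In SAP 8.1.1, define the subset as the narrow search of both queries plus PT 10029332, and footnote the addition on each output.
2. Keep the definition, repeat Tables 14.3__4.4.1 and 14.3__4.4.2 with that PT added as a sensitivity analysis, and list any subject who enters only through it.

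In either case, add a sentence on why the narrow search was chosen, which the SAP does not explain. Leave Table 14.3__1.2.2.13 as the standard narrow search.

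The cost of option 1 is a line of text and one code in the program, and the vitamin subset is then no longer the unmodified narrow search. The cost of option 2 is one extra pair of tables and a short listing.

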12.1.4 Adverse Events of Special Interest

Adverse events of special interest (AESI) for LCIG are:

- Risks of PEG-J insertion
- Long-term complications of PEG-J
- Device associated gastrointestinal disorders during long-term therapy

- Cardiovascular fatalities
- Aspiration including aspiration pneumonia
- A diagnosis of peripheral polyneuropathy; axonal, demyelinating or mixed type
- Possible symptoms of peripheral polyneuropathy such as sensory disturbances or loss of strength, which from their course and clinical presentation or from their response to medication could be precursors of polyneuropathy
- Clinically significant weight loss

A standard panel of examinations will be suggested to the Investigators if one of the study subjects develops signs and symptoms of polyneuropathy. The panel should be considered as a basic recommendation and the selection of additional diagnostic tools is at the discretion of the Investigator, depending on the clinical presentation of the individual subject.

For AESIs, serious and nonserious, meeting pre-defined criteria, specific questionnaires will be used to standardize the collection of follow-up information.

All cases of clinically significant weight loss and possible symptoms or precursors of polyneuropathy (serious and non serious) should be reported on the Report for SAEs and AESIs (Yellow Form) to the Sponsor (or an authorized representative) within the expedited timelines applicable for SAEs.

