- AET010 Incidence of TEAEs that have been linked to a device complication by investigators through the Device Complication CRF. A default frequency table by primary SOC and PT will be presented. The primary SOC's are to be ordered alphabetically. Within each SOC, the PT is also to be ordered alphabetically.
- AET011 Incidence of TEAEs within each consecutive 3005 Treatment Year (as defined in Section 6.4.9) will be summarized. A default frequency table by primary SOC and PT will be presented. The primary SOC's are to be ordered alphabetically. Within each SOC, the PT is also to be ordered alphabetically.
- AET012 Incidence of TEAEs within subgroups. A default frequency table by primary SOC and PT will be presented for each subgroup category. The primary SOC's are to be ordered alphabetically. Within each SOC, the PT is also to be ordered alphabetically.
- AET013 Incidence of TEAEs with a fatal outcome will be presented by primary SOC and PT. The primary SOC's are to be ordered alphabetically. Within each SOC, the PT is also to be ordered alphabetically.
- AET014 Prevalence of TEAEs within each consecutive 3005 Treatment Year (as defined in Section 6.4.9) will be summarized. A default frequency table by primary SOC and PT will be presented. The primary SOC's are to be ordered alphabetically. Within each SOC, the PT is also to be ordered alphabetically.

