10.0 Changes to Planned Analyses

10.1 Changes to the Analysis as Laid Down in the Protocol and Amendments

The protocol statistical methods (Section 6.2 and Section 13.3) stated that for the analysis of change from baseline in efficacy measures, each subject's baseline will be their baseline measure in the first LCIG study in which they participated (e.g., Studies S187.3.001, S187.3.002 or S187.3.004). To focus the analysis on the maintenance of efficacy during participation in Study 3005, each subject's baseline value for the analysis of change from

baseline in efficacy measures will be the final value in the preceding open-label study. To provide context, the change in each efficacy measure from initial LCIG infusion to 3005 endpoint will also be determined and summarized.

Protocol Section 12.1.4 identifies the following as adverse events of special interest:

- Risks of PEG-J insertion
- Long-term complications of PEG-J
- Device-associated gastrointestinal disorders during long-term therapy

For consistency with current practice throughout the LCIG development program, these 3 categories have been combined into a single category of procedure and device associated events (Duodopa product specific CMQ).

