10066593	Post procedural sepsis
10066591	Post procedural stroke
10066415	Post procedural swelling
10051182	Postoperative abscess
10054048	Postoperative ileus
10061468	Postoperative wound complication
10036410	Postoperative wound infection
10050173	Prepyloric stenosis
10057765	Procedural complication
10066962	Procedural nausea
10064882	Procedural pain
10036769	Procedural site reaction
10066963	Procedural vomiting
10069889	Product adhesion issue
10054981	Prophylaxis against gastrointestinal ulcer
10049863	Puncture site abscess
10063677	Puncture site infection

Code	Preferred Term
10061926	Purulence
10037569	Purulent discharge
10038063	Rectal haemorrhage
10069839	Respiratory complication associated with device
10039003	Reversal of ileojejunal bypass
10040102	Seroma
10040893	Skin necrosis
10040943	Skin ulcer
10050377	Skin ulcer haemorrhage
10052535	Small intestinal haemorrhage
10041101	Small intestinal obstruction
10041103	Small intestinal perforation
10062263	Small intestinal stenosis
10061550	Small intestinal ulcer haemorrhage
10041133	Small intestine ulcer
10042070	Stitch abscess
10042128	Stomatitis
10050396	Subileus
10042618	Surgical procedure repeated
10044522	Traumatic haematoma
10053476	Traumatic haemorrhage
10067979	Traumatic liver injury
10044546	Traumatic ulcer
10045285	Ulcer
10061577	Ulcer haemorrhage
10070772	Unintentional medical device removal by patient
10046274	Upper gastrointestinal haemorrhage
10056091	Varices oesophageal
10069840	Vascular complication associated with device
10058042	Wound abscess
10054108	Wound evisceration
10048038	Wound infection
10065240	Wound infection bacterial

Code	Preferred Term
10065242	Wound infection fungal
10065243	Wound infection helminthic
10059444	Wound infection pseudomonas
10059442	Wound infection staphylococcal
10065241	Wound infection viral
10070469	Wrong device dispensed
10070468	Wrong device used
10061582	X-ray gastrointestinal tract abnormal
10059691	X-ray with contrast lower gastrointestinal tract
10059705	X-ray with contrast lower gastrointestinal tract abnormal
10048210	X-ray with contrast upper gastrointestinal tract

2. Polyneuropathy: include Guillain-Barre syndrome SMQ (20000131) and peripheral neuropathy SMQ (20000034).

Guillain-Barre Syndrome SMQ (20000131)

Code	Preferred Term	Narrow Search (N)
10057645	Chronic inflammatory demyelinating polyradiculoneuropathy	N
10061811	Demyelinating polyneuropathy	N
10018767	Guillain-Barre syndrome	N
10049567	Miller Fisher syndrome	N
10049460	Abasia	

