10050329	Coronary angioplasty
10052086	Coronary arterial stent insertion
10011077	Coronary artery bypass
10048631	Coronary artery dissection
10011084	Coronary artery embolism

Code	Preferred Term
10052895	Coronary artery insufficiency
10011086	Coronary artery occlusion
10053261	Coronary artery reocclusion
10056489	Coronary artery restenosis
10011089	Coronary artery stenosis
10011091	Coronary artery thrombosis
10059025	Coronary bypass thrombosis
10011101	Coronary endarterectomy
10011105	Coronary ostial stenosis
10049887	Coronary revascularisation
10013428	Dissecting coronary artery aneurysm
10051177	Electrocardiogram Q wave abnormal
10014390	Electrocardiogram ST segment abnormal
10014392	Electrocardiogram ST segment elevation
10049225	Electrocardiogram ST-T segment elevation
10066846	In-stent coronary artery restenosis
10061216	Infarction
10070909	Metabolic cardiomyopathy
10028596	Myocardial infarction
10028600	Myocardial ischaemia
10051624	Myocardial reperfusion injury
10033697	Papillary muscle infarction
10065608	Percutaneous coronary intervention
10066592	Post procedural myocardial infarction
10058144	Postinfarction angina
10036759	Prinzmetal angina
10058151	Pulseless electrical activity
10061501	Scan myocardial perfusion abnormal
10040560	Shock
10049768	Silent myocardial infarction
10049418	Sudden cardiac death
10042434	Sudden death
10058268	Troponin I increased

Code	Preferred Term
10058267	Troponin increased
10058269	Troponin T increased
10049060	Vascular graft occlusion
10047284	Ventricular asystole
10071186	Ventricular dyssynchrony
10047290	Ventricular fibrillation
10047294	Ventricular flutter
10065341	Ventricular tachyarrhythmia
10047302	Ventricular tachycardia

5. Respiratory tract aspiration including aspiration pneumonia/pneumonitis (CMQ 80000103).

Code	Preferred Term
10066728	Acute interstitial pneumonitis
10069351	Acute lung injury
10001029	Acute pulmonary oedema
10001052	Acute respiratory distress syndrome
10001053	Acute respiratory failure
10002974	Apnoea
10002977	Apnoeic attack
10003497	Asphyxia
10003504	Aspiration
10050777	Aspiration bronchial
10003530	Aspiration tracheal
10003531	Aspiration tracheal abnormal
10003598	Atelectasis
10006102	Bradypnoea
10064913	Bronchial disorder
10006438	Bronchial irritation
10006440	Bronchial obstruction
10056695	Bronchial oedema

Code	Preferred Term
10066820	Bronchial secretion retention
10051547	Bronchial ulceration
10067182	Bronchial wall thickening
10049413	Bronchoalveolar lavage

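### The cardiovascular-fatalities category is filled from the MI part of a MACE query, so fatal stroke, heart-failure, pulmonary-embolism and aortic events fall outside it

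*SAP*

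**What the plan says.** Protocol 12.1.4 lists "Cardiovascular fatalities" among the AESIs. It gives no definition and no restriction to coronary events.

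SAP 8.5.1 keeps the category under the same name and sets the entry rule: "TEAEs are included in a category of special interest based on their PT and, in the case of cardiovascular fatalities, their outcome". The outcome must have been reported as fatal on the adverse event form.

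Appendix 12.4 item 4 supplies the terms: "Cardiovascular fatalities: major adverse cardiovascular events (MACE) MI CMQ (80000076) and the outcome of the AE was fatal". Every preferred term (PT) is printed. The category feeds Table 14.3__1.2.2.15 (Safety sample), Table 14.3__1.2.4.10 (US subset) and Listing 14.3__2.7. All three titles refer to cardiovascular fatalities without qualification.

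Two other outputs cover deaths whatever their cause. For AET013, SAP 9.11.1 says: "Incidence of TEAEs with a fatal outcome will be presented by primary SOC and PT". AEL003 lists the subjects who died.

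SAP 10.1 records one change to the AESIs, concerning the PEG-J and device items: "these 3 categories have been combined into a single category of procedure and device associated events". It does not mention cardiovascular fatalities.

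**The concern.** In ordinary use, a cardiovascular death includes death from heart failure and usually death from stroke. Because entry is decided by PT, any cause whose term is not on the list is excluded by rule, however clearly the investigator attributes the death to it.

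This is a single-arm study whose primary statistical objective is long-term safety (Protocol 13.1), and AESI incidence is one of the protocol's specified summaries (Protocol 13.3). There is no comparator against which an omission could cancel, so the count itself is the result. A low or zero figure under an unqualified title would be read as cardiovascular mortality on LCIG.

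**Working it through.** The plan gives no figure to reproduce. The check is to read the item 4 list term by term and follow the entry rule through to the outputs.

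**1. Content of the list (SAP 12.4, item 4).** It prints 61 PTs. Searching it by group gives:

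| Group | PTs found |
|---|---|
| Stroke or other cerebrovascular | 0 |
| Cardiac or ventricular failure | 0; nearest are "Cardiogenic shock", Metabolic cardiomyopathy and Shock |
| Pulmonary embolism | 0 |
| Aortic | 0 |
| Embolism, thrombosis or aneurysm of any kind | 4, all coronary |
| Arrest, sudden death, agonal rhythm, ventricular arrhythmia | 12, for example "Sudden cardiac death" |

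The remaining terms are mainly coronary disease and procedures, infarction and ischaemia, cardiac enzymes and ECG findings.

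**2. A comparison inside the appendix.** The procedure and device list (item 1) holds three parallel terms: post-procedural myocardial infarction, post-procedural pulmonary embolism, and "Post procedural stroke". Only the infarction term is repeated in item 4. A PT may sit in more than one category (Dysphagia is in items 2, 3 and 5). A fatal post-procedural stroke would therefore be counted as a procedure or device event and not also as a cardiovascular fatality.

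**3. Whether such a death could enter another way.** Protocol 12.1.1 reserves the fatal outcome for the event that caused the death. A death attributed to stroke or heart failure should therefore carry fatal on that event and not on a co-existing one. It enters item 4 only if the investigator reports the cause in listed terms, such as cardiac arrest, cardiogenic shock or sudden death.

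**4. Size.** The documents give no number or causes of death, so the size can only be expressed as a function of an assumed share. Let D be the number of cardiovascular deaths in the ordinary sense and f the share coded to the missing groups. Then

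counted = D × (1 − f).

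For illustration, with D = 10 (assumed):

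| f (assumed) | Calculation | Counted |
|---|---|---|
| 0 | 10 × 1.0 | 10 |
| 10% | 10 × 0.9 | 9 |
| 30% | 10 × 0.7 | 7 |
| 50% | 10 × 0.5 | 5 |

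These rows show how the rule behaves. They do not estimate what will happen in this study.

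**The case against.** The strongest reply has four parts.

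- **The protocol supplies only a label.** A reader might infer that the SAP contradicts a protocol definition covering every cardiovascular death. There is no such definition, and the sponsor may always have meant a coronary and sudden-death category. This stands: the point rests on the ordinary meaning of the label, not on a breached definition.
- **No death is hidden.** A reader might infer that fatal strokes or heart-failure deaths vanish from the report. They do not. AET013 shows fatal treatment-emergent events by organ class and term, for the Safety sample and the US subset, and AEL003 lists deaths. This stands too, and it limits the problem to one category. But neither output gives a cardiovascular total, so readers would have to build one and might find that it disagrees with the titled table.
- **The list is wider than infarction.** It is, and some heart-failure or embolic deaths would be captured through arrest or sudden-death terms. That reduces the loss without removing it.
- **The definition is disclosed, and other AESIs also became term lists without an entry in SAP 10.1.** It is true that the appendix prints every term, and that weight loss and aspiration were handled in the same way. Turning an undefined label into a list is not clearly a change that has to be declared. The direction differs, however. Those two lists reach beyond their labels (decreased appetite under weight loss; pneumonia and pyrexia under aspiration), whereas item 4 stops short of its label.

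**Conclusion.** The point holds as one of scope and labelling in a descriptive safety output. A mortality category named in the protocol is filled by a rule that excludes fatal cardiac-failure, cerebrovascular, pulmonary-embolism and aortic events, while its tables and listing carry an unqualified title.

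The exclusion is certain from the printed list. Its numerical effect is not known: the category captures 1 − f of cardiovascular deaths, and f may be zero. A reader might infer a particular percentage undercount, but the documents give no causes of death to support one.

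The conclusion assumes that cardiovascular is read in its ordinary sense and that investigators assign the fatal outcome as Protocol 12.1.1 directs. No hypothesis test is affected.

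**What to change.** Add to item 4 a fixed list, printed in advance, of cerebrovascular, cardiac-failure, pulmonary-embolism and aortic PTs, applied with the same fatal-outcome condition. Ventricular arrhythmia terms are already present and need no addition. Keep the count from the current MI list as a sub-row in both tables, and state the definition in SAP 10.1. Combining queries is not new to this plan: the polyneuropathy category already joins two.

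If the sponsor prefers to keep the present list, the minimum is to retitle the category, both tables and the listing as MI/sudden-cardiac fatalities, and to declare the narrower scope in SAP 10.1.

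A fixed list is preferable to case-by-case selection because it can be reproduced. Blinded review would add little in a single-arm, open-label study.

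The cost is a slightly longer term list and a count that may be higher, or may differ from other studies in the programme. The sub-row preserves that comparison.
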